4.2.3.3 Future Biomedical Research

The Sponsor will conduct Future Biomedical Research on specimens collected for future biomedical research during this clinical trial. This research may include genetic analyses (DNA), gene expression profiling (RNA), proteomics, metabolomics (serum, plasma) and/or the measurement of other analytes.

Such research is for biomarker testing to address emergent questions not described elsewhere in the protocol (as part of the main trial) and will only be conducted on specimens from appropriately consented subjects. The objective of collecting specimens for Future Biomedical Research is to explore and identify biomarkers that inform the scientific understanding of diseases and/or their therapeutic treatments. For instance, exploratory pharmacogenetic (PGt) studies may be performed if significant Pharmacokinetic/Pharmacodynamic (PK/PD) relationships are observed or adverse events are identified. Genomic markers of disease may also be investigated. Such retrospective pharmacogenetic studies will be conducted with appropriate biostatistical design and analysis and compared to PK/PD results or clinical outcomes. Any significant PGt relationships to outcome would require validation in future clinical trials. The overarching goal is to use such information to develop safer, more effective drugs/vaccines, and/or to ensure that subjects receive the correct dose of the correct drug/vaccine at the correct time. The details of this Future Biomedical Research sub-trial are presented in Section 12.2 - Collection and Management of Specimens for Future Biomedical Research. Additional informational material for institutional review boards/ethics committees (IRBs/ERCs) and investigational site staff is provided in Section 12.3.

4.3 Benefit/Risk

A subset of subjects will receive Prevnar 13™ which is the standard of care and is serving as the active comparator in this study. V114 is aimed at providing comparable immune responses to Prevnar 13™ for the shared serotypes while providing additional coverage for the 2 serotypes (22F and 33F) unique to V114. It is unknown if the investigational V114 will have the same benefit as Prevnar 13™. As a possible rescue medication in this study, subjects who fail to achieve adequate immune responses to serotype 19A (individually) and/or to 4 or more serotypes in common between Prevnar 13™ and V114 following the

third dose of study vaccine will be offered an additional dose of licensed pneumococcal conjugate vaccine between 9 and 12 months of age. (See section 5.6 Rescue Medications & Supportive Care for additional details).

Additional details regarding specific benefits and risks for subjects participating in this clinical trial may be found in the accompanying Investigators Brochure (IB) and Informed Consent documents.

5.0 METHODOLOGY

5.1 Entry Criteria

5.1.1 Diagnosis/Condition for Entry into the Trial

Healthy male and female subjects between the ages of 18 and 49 years of age for the adult cohort AND between 42 and 90 days (approximately 2 months of age) for the infant cohort (inclusive) will be enrolled in this trial.

5.1.2 Subject Inclusion Criteria

In order to be eligible for participation in this trial, the subject must:

Adult Cohort (Stage 1):

1. Be an adult, age 18 to 49 years and in good health. Any underlying chronic illness must be documented to be in stable condition.
2. Is able to read, understand, and complete the study questionnaires (i.e., the VRC).
3. Be able to attend all scheduled visits and to comply with the study procedures.
4. Meet one of the following categories:
 - a) The subject is a male.
 - b) The subject is a female who is not of reproductive potential, defined as a female who either: (1) is postmenopausal (defined as at least 12 months with no menses in women \geq 45 years of age); (2) has had a hysterectomy and/or bilateral oophorectomy, bilateral salpingectomy, or bilateral tubal ligation/occlusion at least 6 weeks prior to screening; OR (3) has a congenital or acquired condition that prevents childbearing.
 - c) The subject is a female who is of reproductive potential and agrees to avoid becoming pregnant while receiving study vaccine and for 6 weeks after the last dose of study vaccine by complying with one of the following: (1) practice abstinence[†] from heterosexual activity OR (2) use (or have her partner use) acceptable contraception during heterosexual activity. Acceptable methods of contraception are[‡]:

Single method (one of the following is acceptable):

- intrauterine device (IUD)
- vasectomy of a female subject's male partner
- contraceptive rod implanted into the skin

Combination method (requires use of two of the following):

- diaphragm with spermicide (cannot be used in conjunction with cervical cap/spermicide)
- cervical cap with spermicide (nulliparous women only)
- contraceptive sponge (nulliparous women only)
- male condom or female condom (cannot be used together)
- hormonal contraceptive: oral contraceptive pill (estrogen/progestin pill or progestin-only pill), contraceptive skin patch, vaginal contraceptive ring, or subcutaneous contraceptive injection

[†]Abstinence (relative to heterosexual activity) can be used as the sole method of contraception if it is consistently employed as the subject's preferred and usual lifestyle and if considered acceptable by local regulatory agencies and ERCs/IRBs. Periodic abstinence (e.g., calendar, ovulation, sympto-thermal, post-ovulation methods, etc.) and withdrawal are not acceptable methods of contraception.

[‡]If a contraceptive method listed above is restricted by local regulations/guidelines, then it does not qualify as an acceptable method of contraception for subjects participating at sites in this country/region.

5. Understand the study procedures, alternate treatments available and risks involved with the study, and voluntarily agree to participate by giving written informed consent. The subject may also provide consent for FBR. However, the subject may participate in the main trial without participating in the FBR.

Infant Cohort (Stage 2 - Parts I and II):

1. Be healthy (based on medical history and physical examination) male or female infant approximately 2 months of age (42 days to 90 days), inclusive.
2. Have a parent/legal guardian who understands the study procedures, alternate treatments available, and risks involved with the study.

3. Have a parent/legal guardian who is able to read, understand, and complete the VRC and voluntarily agree to participate by giving written informed consent.
4. Be able to attend all scheduled visits and to comply with the study procedures.
5. Have a parent/legal guardian that has access to a telephone.
6. The subjects' parent/legal guardian may also provide written informed consent for FBR. However, the subject may participate in the main trial without participating in FBR.

5.1.3 Subject Exclusion Criteria

The subject must be excluded from participating in the trial if the subject:

For items with an asterisk (*), if the subject meets these exclusion criteria, the Day 1 Visit may be rescheduled for a time when these criteria are not met.

Adult Cohort (Stage 1):

1. Has had prior administration of any pneumococcal vaccine.
2. Has a history of invasive pneumococcal disease (positive blood culture, positive cerebrospinal fluid culture, or other sterile site) or known history of other culture-positive pneumococcal disease.
3. Has known hypersensitivity to any component of the pneumococcal conjugate vaccine, or any diphtheria toxoid-containing vaccine.
4. Has known or suspected impairment of immunological function, history of congenital or acquired immunodeficiency (e.g. splenomegaly), documented HIV infection, functional or anatomic asplenia, history of autoimmune disease including multiple sclerosis (MS), MS-like disease, systemic lupus erythematosus, polymyositis, inclusion body myositis, dermatomyositis, Hashimoto's thyroiditis, Sjogren's syndrome, rheumatoid arthritis, or other autoimmune disorders.
5. Has a coagulation disorder contraindicating intramuscular vaccinations.
6. *Has received systemic corticosteroids (equivalent of ≥ 2 mg/kg total daily dose of prednisone or ≥ 20 mg/d for persons weighing > 10 kg) for ≥ 14 consecutive days and has not completed treatment at least 30 days prior to study entry. Has received systemic corticosteroids exceeding physiologic replacement doses (~ 5 mg/d prednisone equivalent) within 14 days prior to the first vaccination.
7. *Has received other licensed non-live vaccines within the 14 days before receipt of study vaccine. (Exception: Inactivated influenza vaccine may be administered

during the study but must be given at least 2 weeks prior to receipt of the study vaccine or at least 4 weeks after receipt of the study vaccine).

8. *Has received a licensed live virus vaccine within 30 days prior of receipt of study vaccine.
9. *Had a recent febrile illness ($\geq 100.4^{\circ}\text{F}$ [$\geq 38.0^{\circ}\text{C}$] oral or equivalent) or received antibiotic therapy for any acute illness occurring within 72 hours before receipt of study vaccine.
10. Has received a blood transfusion or blood products, including immunoglobulins within the 6 months before receipt of study vaccine or is scheduled to receive a blood transfusion or blood product within 30 days of receipt of study vaccine. Autologous blood transfusions are not considered an exclusion criterion.
11. Has participated in another clinical study of an investigational product within 2 months before the beginning of or any time during the duration of the current clinical study. Subjects enrolled in observational studies may be included; these will be reviewed on a case-by-case basis for approval by the SPONSOR.
12. Is breast-feeding.
13. Cannot be adequately followed for safety according to the protocol.
14. Is unlikely to adhere to study procedures, keep appointments, or is planning to relocate during the study.
15. Has any other reason that, in the opinion of the investigator, may interfere with the evaluation required by the study.
16. Is or has an immediate family member (e.g. spouse, parent/legal guardian, sibling, or child) who is investigational site or sponsor staff directly involved with this trial.

For items with an asterisk (*), if the subject meets these exclusion criteria, the Day 1 Visit may be rescheduled for a time when these criteria are not met.

Infant Cohort (Stage 2 - Parts I and II):

1. Had prior administration of any pneumococcal vaccine.
2. Has a known hypersensitivity to any component of the pneumococcal conjugate vaccine, or any diphtheria toxoid-containing vaccine.
3. *Had a recent febrile illness (rectal temperature $\geq 38.1^{\circ}\text{C}$ [$\geq 100.5^{\circ}\text{F}$] or axillary temperature $\geq 37.8^{\circ}\text{C}$ [$\geq 100.0^{\circ}\text{F}$]) occurring within 72 hours of receipt of study vaccine.

4. Has a known or suspected impairment of immunological function.
5. Has a history of congenital or acquired immunodeficiency (e.g. splenomegaly).
6. Has or his/her mother has a documented Human immunodeficiency virus (HIV) infection.
7. Has or his/her mother has a documented hepatitis B surface antigen - positive.
8. Has functional or anatomic asplenia.
9. Has a history of failure to thrive.
10. Has a coagulation disorder contraindicating intramuscular vaccination.
11. Has a history of autoimmune disease including systemic lupus erythematosus, anti-phospholipid syndrome, Behcet's disease, autoimmune thyroid disease, polymyositis and dermatomyositis, scleroderma, type I diabetes mellitus, and other autoimmune disorders.
12. Has a known neurologic or cognitive behavioral disorder, including encephalitis/myelitis, acute disseminating encephalomyelitis, pervasive development disorder, and related disorders.
13. Has received systemic corticosteroids (equivalent of ≥ 2 mg/kg total daily dose of prednisone or ≥ 20 mg/d for persons weighing > 10 kg) for ≥ 14 consecutive days and has not completed treatment at least 30 days prior to study entry. Has received systemic corticosteroids within 14 days prior to the first vaccination or is expected to require systemic corticosteroids within 30 days after each vaccination during conduct of the study.
14. Has received other licensed non-live vaccines within the 14 days before receipt of study vaccine.
15. Has received a licensed live virus vaccine within the 30 days prior of receipt of study vaccine.
16. Had prior receipt of a blood transfusion or blood products, including immunoglobulins.
17. Has participated in another clinical study of an investigational product before the beginning or anytime during the duration of the current clinical study. Subjects enrolled in observational studies may be included; these will be reviewed on a case-by-case basis for approval by the SPONSOR.

18. Has a history of invasive pneumococcal disease (positive blood culture, positive cerebrospinal fluid culture, or other sterile site) or known history of other culture positive pneumococcal disease.
19. Cannot be adequately followed for safety according to the protocol plan.
20. Has a parent/legal guardian who is unlikely to adhere to study procedures, keep appointments, or is planning to relocate during the study.
21. Has any other reason that in the opinion of the investigator may interfere with the evaluation required by the study.
22. Is or has an immediate family member (e.g., spouse, parent/legal guardian, sibling or child) who is investigational site or sponsor staff directly involved with this trial.

5.2 Trial Vaccination(s)

The vaccines to be used in this trial are outlined below in [Table 1](#) and [Table 2](#).

Table 1 Trial Vaccination – Adult Cohort

Vaccination at Visit 1 (18 to 49 years of age) with 0.5mL given IM			
Vaccine	Serotypes 1, 3, 4, 5, 6A, 6B, 7F, 9V, 14 18C, 19F, 19A, 22F, 23F and 33F	MAPA	Use in Study
V114 medium	2 µg; except 6B (4 µg)	125 µg	Investigational
V114 high	4 µg; except 6B (8 µg)	250 µg	Investigational
V114 medium with an alternative carrier protein	2 µg; except 6B (4 µg)	125 µg	Investigational
V114 high with an alternative carrier protein	4 µg; except 6B (8 µg)	250 µg	Investigational

Table 2 Trial Vaccination – Infant Cohort

Vaccination at Visit 1 (~2 months of age), Visit 2 (~4 months of age), Visit 3 (~6 months of age) and Visit 5 (~12 to 15 months of age) with 0.5-mL given IM			
Vaccine	Serotypes 1, 3, 4, 5, 6A, 6B, 7F, 9V, 14 18C, 19F, 19A, 22F, 23F and 33F	MAPA	Use in Study
V114 medium	2 µg; except 6B (4 µg)	125 µg	Investigational
V114 high	4 µg; except 6B (8 µg)	250 µg	Investigational
V114 medium with an alternative carrier protein	2 µg; except 6B (4 µg)	125 µg	Investigational
V114 high with an alternative carrier protein	4 µg; except 6B (8 µg)	250 µg	Investigational
Prevnar 13™	Prevnar 13™		Active comparator

Trial vaccination is given on the day of randomization or as close as possible to the date on which the subject is allocated/assigned.

The investigator shall take responsibility for and shall take all steps to maintain appropriate records and ensure appropriate supply, storage, handling, distribution and usage of trial treatments in accordance with the protocol and any applicable laws and regulations.

5.2.1 Dose Selection

5.2.1.1 Dose Selection (Preparation)

The rationale for selection of doses to be used in this trial is provided in Section 4.0 – Background & Rationale. There are no specific calculations or evaluations required to be performed in order to administer the proper dose to each subject.

5.2.2 Timing of Dose Administration

For adult cohort (Stage 1), V114 will be administered as a 0.5-mL intramuscular injection at Visit 1.

For the infant cohorts (Stage 2, Parts I and II), V114 or Prevnar 13™ will be administered as a 0.5-mL intramuscular injection at Visit 1 (approximately 2 months of age [≥ 42 or ≤ 90 days of age]), Visit 2 (4 months of age to 1 day prior to 5 months of age), Visit 3 (6 months of age to 1 day prior to 7 months of age) and Visit 5 (12 months of age to 1 day prior to 16 months of age). Other pediatric vaccines will be administered concomitantly on the same day as study vaccine according to the recommended schedule. Concomitant oral vaccines may be

administered prior to the study vaccine and other injectable concomitant vaccines. Precautions must be taken to prevent choking during the administration of oral vaccines. Concomitant injectable vaccines should be administered on the same day as study vaccine and after the study vaccine has been administered. To avoid any confounding results, non-study injectable vaccines should not be administered in the same limb as study vaccine.

5.2.3 Trial Blinding/Masking

A double-blind/masking technique will be used. V114 will be dispensed in a blinded fashion by an unblinded pharmacist or qualified trial site personnel. The subject, the investigator and Sponsor personnel or delegate(s) who are involved in the vaccine administration or clinical evaluation of the subjects are unaware of the group assignments.

In-house blinding procedures will be used. Note: Because the study vaccine and Prevnar 13™ have a different appearance, a member of the study site staff will be unblinded for the purpose of receiving, maintaining, and preparing/administering the study vaccine. In order to avoid bias, the unblinded study personnel will have no further contact with study subjects for any study-related procedures/assessments after administration of study vaccines, which includes all safety follow up procedures. Contact between subjects and unblinded study personnel after vaccination administration is strictly prohibited.

For this Phase I-II study, MRL statisticians and an MRL statistical programmer assigned to the protocol will be unblinded throughout the duration of the study to facilitate reviews of the safety data by the eDMC, and the performing of the 2 planned interim analyses of the immunogenicity and safety data. All other MRL employees directly involved with the conduct of this trial will remain blinded to the subject level treatment assignment, and will receive only group level summaries of immunogenicity and safety data from the analyses.

See Section 7.1.4.2, Blinding/Unblinding, for a description of the method of unblinding a subject during the trial, should such action be warranted.

5.3 Randomization or Vaccine Allocation

Randomization will occur centrally using an interactive voice response system / integrated web response system (IVRS/IWRS). There are 4 V114 adult vaccination arms. Subjects will be assigned randomly in a 1:1:1:1 ratio to each of the 4 V114 vaccination groups in Stage 1, for the adult cohort. The infant cohort (Stage 2) will have 5 vaccination arms during which subjects will be randomly assigned in a 1:1:1:1:1 ratio to each of the 4 V114 vaccination groups or control (Prevnr 13™), respectively. Each formulation of V114 will be first evaluated in a small number of infants (10/arm) during Part I before initiating Part II, which will enroll the remainder of the infant cohort.

5.4 Stratification

No stratification based on age, sex or other characteristics will be used in this trial.

5.5 Concomitant Medications/Vaccinations (Allowed & Prohibited)

Medications or vaccinations specifically prohibited in the exclusion criteria are not allowed during the ongoing trial. If there is a clinical indication for any medication or vaccination specifically prohibited during the trial, discontinuation from trial therapy or vaccination may be required. The investigator should discuss any questions regarding this with the Sponsor Clinical Director. The final decision on any supportive therapy or vaccination rests with the investigator and/or the subject's primary physician. However, the decision to continue the subject on trial therapy or vaccination schedule requires the mutual agreement of the investigator, the Sponsor and the subject.

Any concurrent medication or medical treatment must be recorded on the appropriate electronic case report form (eCRF). During the influenza season, it is anticipated that study subjects 6 months of age and older may be given an influenza vaccine. Influenza vaccine should be administered either 2 weeks prior to or 4 weeks after the administration of the study vaccine.

If a medical condition requires the use of immunoglobulin, blood, or blood products during a subject's participation in this study, one of the individuals listed on the SPONSOR Contact Information page must be notified immediately and any such use must be documented on the appropriate eCRF.

Adults:

Subjects should not receive systemic corticosteroids during the study, unless medically required and with a goal of down-titrating/discontinuing as soon as medically feasible. Short-term (< 14 days) or alternate day administration at low to moderate doses (equivalent of < 2 mg/kg total daily dose of prednisone or < 20 mg/d for persons weighing > 10 kg) are approaches to mitigate potential risks associated with immunosuppression.

Subject should not receive systemic corticosteroids (equivalent of > 2 mg/kg total daily dose of prednisone or > 20 mg/d for persons weighing > 10 kg for > 14 consecutive days) following vaccine administration through the VRC specified follow-up period.

Intra-articular or soft-tissue (e.g., bursa, tendon) injections of steroids are permitted. Topical, ophthalmic and inhaled steroids are also permitted.

For the adult cohort (Stage 1), V114 will be administered at Visit 1. No other investigational compound or device or prohibited concomitant vaccines (see Section 5.1.3 Subject Exclusion Criteria) may be administered at any time during this study without prior approval by the SPONSOR.

Infants:

For the infant cohort (Stage 2, Parts I and II) the study vaccines (V114 and Prevnar 13TM) will be administered at 2, 4, 6, and 12 to 15 months of age. On the day of vaccination, it is

important to record the use of any analgesic or antipyretic use on the VRC and appropriate eCRF.

Subjects should not receive systemic corticosteroids (equivalent of ≥ 2 mg/kg total daily dose of prednisone or ≥ 20 mg/d for persons weighing >10 kg for ≥ 14 consecutive days) starting from 30 days prior to vaccination through 30 days after each vaccination. Topical, ophthalmic and inhaled steroids are permitted.

Other pediatric vaccines will be administered concomitantly according to the recommended schedule. These concomitant non-study vaccinations will be recorded on the appropriate eCRF.

Concomitant vaccines (oral or injectable) should be administered on the same day as study vaccine. Concomitant oral vaccines may be administered prior to the study vaccine and other injectable concomitant vaccines. Precautions must be taken to prevent choking during the administration of oral vaccines. Other pediatric injectable vaccines administered concomitantly should be given after the study vaccine. To avoid any confounding results, non-study injectable vaccines should not be administered in the same limb as study vaccine. Documentation of which limb was used for the administration of study vaccine should be recorded on the appropriate eCRF. As the study is reporting injection-site AEs from the study vaccine (and not from the concomitant vaccines), this information should also be recorded on the VRC to inform the parent/legal guardian of the appropriate limb to monitor for AEs ONLY related to the study vaccine.

No other investigational compound or device may be administered at any time during this study without prior approval by the SPONSOR.

5.6 Rescue Medications & Supportive Care

Infant subjects who fail to achieve adequate serologic responses following the third dose of study vaccine will be offered an additional dose of licensed pneumococcal conjugate vaccine outside of this protocol. Any study subject with serotype-specific pneumococcal IgG (as measured by Pn ECL assay) below 0.35 μ g/mL for serotype 19A (individually) and/or 4 or more serotypes in common between V114 and Prevnar 13TM at 1 month PD3, will be given one dose of licensed pneumococcal conjugate vaccine as soon as possible after serological results are available. All subjects who meet the rescue criterion must be discontinued from the study prior to administering the additional dose of licensed pneumococcal conjugate vaccine. The discontinuation date should be the date the parent/legal guardian was notified of the child's meeting the rescue criterion. Adverse events or changes to medical history occurring after the 14 days of safety follow up for Dose 3 and the discontinuation should be reported in the database; no additional immunogenicity blood sample should be drawn. If an SAE occurs between the 14 days of safety follow up for Dose 3 and the discontinuation, that event must be reported. The serologic threshold value of 0.35 μ g/mL was recommended by a WHO expert panel as an acceptable threshold value for evaluating the clinical performance of pneumococcal conjugate vaccines in infants [3],[4]. Adequate treatment provisions,

including epinephrine, should be available for immediate use should an anaphylactic or anaphylactoid reaction occur.

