3.2 Secondary Objective(s) & Hypothesis(es)

Stage 1 - (Adults ONLY)

1. To evaluate the serotype-specific IgG GMCs and fold-rises from baseline of V114 medium and V114 high at 1 month postvaccination.

Stage 2 - Parts I and II (Infants ONLY)

1. To evaluate the serotype-specific IgG response rates of V114 medium, V114 high, and Prevnar 13™, and the differences in IgG response rates between each of these V114 formulations and Prevnar 13™ for the 13 common serotypes at 1 month PD3, pre-dose 4, and 1 month PD4.
 - Serotype-specific IgG response rates will be based on the proportion of recipients of V114 and Prevnar 13™ achieving the World Health Organization (WHO)-accepted threshold value of 0.35µg/mL using the Pn ECL assay for each V114 formulation and Prevnar 13™.
2. To evaluate the serotype-specific IgG GMCs of V114 medium, V114 high, and Prevnar 13™, and the IgG GMC ratios between each of these V114 formulations and Prevnar 13™ for the 13 common serotypes at pre-dose 4 and 1 month PD4.

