5.8 Subject Withdrawal/Discontinuation Criteria

Subjects may withdraw consent at any time for any reason or be dropped from the trial at the discretion of the investigator should any untoward effect occur. In addition, a subject may be withdrawn by the investigator or the Sponsor if enrollment into the trial is inappropriate, the trial plan is violated, or for administrative and/or other safety reasons. Specific details regarding discontinuation or withdrawal procedures; including specific details regarding withdrawal from Future Biomedical Research, are provided in Section 7.1.4 – Other Procedures.

In this trial, a subject may discontinue from vaccination but continue to participate in the regularly scheduled activities, as long as the subject does not withdraw consent. Discontinuation from vaccination is permanent. Once a subject has discontinued vaccination, even though he/she continues to be monitored in the trial, he/she shall not be allowed to begin vaccination again.

A subject must be discontinued from the trial for any of the following reasons:

- The subject or legal representative (such as a parent or legal guardian) withdraws consent.
- The subject has a medical condition or personal circumstance which, in the opinion of the investigator and/or SPONSOR, places the subject at unnecessary risk through continued participation in the trial or does not allow the subject to adhere to the requirements of the protocol.
- In stage 2 (Parts I and II), any infant subject that fails to achieve adequate serologic responses, as described in Section 5.6, will be discontinued from the study.

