Endpoint/Variable (Description, Time Point)	Statistical Method	Analysis Population	Missing Data Approach
Primary Objectives			
PD3 GMCs, for the 15 serotypes in V114 and the 13 serotypes in Prevnar 13™ [V114 medium, V114 high, Prevnar 13™] (Infant Primary Objective #2)	
 • Within-group GMCs and 95% CI • GMC ratio (V114 arm/Prevnar 13™) and 95% CI (2-sample t-test) for common serotypes 	Infant Per-Protocol	Missing data will be dropped
PD3 GMCs, for the 15 serotypes in V114 and the 13 serotypes in Prevnar 13™ [V114 medium, V114 high, Prevnar 13™] (Infant Primary Objective #2)	
 • Within-group GMCs and 95% CI • GMC ratio (V114 arm/Prevnar 13™) and 95% CI (2-sample t-test) for common serotypes 	Infant FAS [Supportive]	Missing data will be dropped
Secondary Objectives			
PD3, pre-dose 4, PD4 % \geq 0.35, for the 15 serotypes in V114 and the 13 serotypes in Prevnar 13™ [V114 medium, V114 high, Prevnar 13™] (Infant Secondary Objective #1)	
 • Within-group %\geq0.35 and 95% CI • Difference in %\geq0.35 (V114 arm-Prevnar 13™) and 95% CI (M&N) for common serotypes 	Infant Per-Protocol	Missing data will be dropped
Pre-dose 4 and PD4 GMCs, for the 15 serotypes in V114 and the 13 serotypes in Prevnar 13™ [V114 medium, V114 high, Prevnar 13™] (Infant Secondary Objective #2)	
 • Within-group GMCs and 95% CI • GMC ratio (V114 arm/Prevnar 13™) and 95% CI (2-sample t-test) for common serotypes 	Infant Per-Protocol	Missing data will be dropped
PD1 GMCs and fold-rises from baseline, for 15 serotypes in V114 and the 13 serotypes in Prevnar 13™ [V114 medium, V114 high] (Adult Secondary Objective #1)	
 • Within-group GMCs and 95% CI • Within-group fold-rises from baseline and 95% CI 	Adult Per-Protocol	Missing data will be dropped

The strategy to address multiplicity issues is described in Section 8.7, Interim Analyses and in Section 8.8, Multiplicity.

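### The pre-dose 4 and PD4 secondary results, mainly for 19A, come from infants selected on PD3 response, and no supportive analysis accounts for it

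*Combined protocol and SAP*

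**What the plan says.** Section 5.6 sets the trigger at PD3 IgG below 0.35 µg/mL "for serotype 19A (individually) and/or 4 or more serotypes in common between V114 and Prevnar" 13. On the consequence it is explicit: "All subjects who meet the rescue criterion must be discontinued from the study". It adds that "no additional immunogenicity blood sample should be drawn". Section 5.8 repeats the exit and does not make it depend on accepting the extra dose: "any infant subject that fails to achieve adequate serologic responses, as described in Section 5.6, will be discontinued from the study".

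On timing, Section 4.3 says these infants "will be offered an additional dose of licensed pneumococcal conjugate vaccine between 9 and 12 months of age". The flow chart in Section 6.0 places the pre-dose 4 draw at Visit 5, from 12 months of age to a day short of 16 months, so exit normally comes first. Section 5.9 allows no replacement.

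The later time points carry secondary objectives. Section 3.2 asks for GMCs and GMC ratios "for the 13 common serotypes at pre-dose 4 and 1 month PD4", and for response rates at the same visits. The Table 4 row headed "Pre-dose 4 and PD4 GMCs, for the 15 serotypes in V114 and the 13 serotypes" lists the infant per-protocol population only, and its missing-data entry is "Missing data will be dropped". The response-rate row is the same. The Full Analysis Set appears as supportive only for the PD3 GMCs (Section 8.5.1 and Table 4). Section 8 does not mention rescue.

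**The concern.** The later 19A analysis is conditioned on the earlier 19A value. An infant below 0.35 at PD3 is likely to be lower than average at pre-dose 4 and PD4 too, and such infants are removed by rule. Two effects follow.

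- Within each arm, the later 19A GMC and response rate are shifted upward, even if the arms are identical.
- If the arms differ in PD3 19A, the weaker arm loses more of its low responders, and the contrast with Prevnar 13 is generally pulled toward no difference. The ratio is untouched only if both the PD3 distributions and the PD3-to-later relationship are the same in the two arms.

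At stake is how the secondary tables are read. The reader sees a ratio or rate difference among infants who did not meet the rescue criterion and may take it for the contrast between the arms as randomised. Extending the Full Analysis Set would not help, because the samples do not exist.

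**Working it through.** **Inputs from the plan (Section 8.9).** 45 evaluable infants per arm at PD3; SD of log concentration 0.8 to 1.4; GMC 1 to 3 µg/mL. The footnotes call these representative of V114-003 but do not give them for 19A. The cut is 0.35.

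**Assumed.** PD3-to-later correlation ρ, waning, and between-serotype correlation. The documents give none of these.

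**Plan's own figure.** Two-sample t power, 45 per arm, SD 1.0, 2-fold difference, one-sided 0.05: noncentrality ln 2/√(2/45) = 3.29 on 88 df gives 94.7%, as stated. The scale and n are therefore read correctly.

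**1. Exits on the 19A trigger.** Share = Φ(z), with z = ln(0.35/GMC)/SD. Example, GMC 1, SD 1.0: z = −1.050, Φ = 0.147, and 45 × 0.147 = 6.6.

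| SD | GMC 1 | GMC 2 | GMC 3 |
|---|---|---|---|
| 0.8 | 4.3 | 0.7 | 0.2 |
| 1.0 | 6.6 | 1.8 | 0.7 |
| 1.2 | 8.6 | 3.3 | 1.7 |
| 1.4 | 10.2 | 4.8 | 2.8 |

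Both triggers together, simulated with 13 serotypes, SD 1.0 and between-serotype correlation 0.3 to 0.6: 0.8 to 1.1 exits of 45 if all GMCs are 3; 2.5 to 3.0 if all are 2; 7.0 to 7.1 if 19A is 1 and the rest 2.

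**2. Within-arm shift at PD4 (19A trigger only).** The mean log among infants kept rises by ρ·SD·λ, with λ = φ(z)/(1 − Φ(z)). For ρ 0.3 to 0.7 the GMC is inflated by 8 to 21% (GMC 1, SD 1.0; λ = 0.270), 3 to 7% (GMC 2, SD 1.0; λ = 0.091) and under 1% (GMC 3, SD 0.8; λ = 0.011).

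**3. PD4 ratio.** The bias on the log scale is the difference between the two arms' shifts. The SE uses the retained n and the truncated variance SD²(1 − ρ²λ(λ − z)). Example, GMC 1 against 2, SD 1.0, ρ = 0.5: bias = 0.5 × (0.270 − 0.091) = 0.089; SE = 0.214; the estimate is 0.50 × exp(0.089) = 0.547, 95% CI about 0.36 to 0.84, and bias/SE = 0.42.

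| Arms (true ratio) | SD | ρ 0.3 | ρ 0.5 | ρ 0.7 |
|---|---|---|---|---|
| 1 v 2 (0.50) | 1.0 | 0.528 | 0.547 | 0.567 |
| 1 v 2 (0.50) | 1.2 | 0.535 | 0.559 | 0.585 |
| 1 v 2 (0.50) | 1.4 | 0.540 | 0.569 | 0.599 |
| 2 v 3 (0.667) | 1.0 | 0.677 | 0.684 | 0.691 |
| 2 v 3 (0.667) | 1.4 | 0.688 | 0.702 | 0.717 |

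Bias/SE is 0.24 to 0.63 for 1 v 2 and 0.07 to 0.25 for 2 v 3.

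**4. Pre-dose 4 response rate** (bivariate normal, SD 1.0, 2-fold waning, ρ 0.5 to 0.9). At GMC 1 a true 63.9% reads 69.5 to 74.5%; at GMC 2 a true 85.3% reads 86.8 to 88.7%. The difference of −21.4 points reads −17.4 to −14.2. For GMC 2 against 3, −7.4 reads −6.4 to −5.4. PD4 rates hardly move if dose 4 boosts 3-fold: −1.4 reads −1.0 to −0.3.

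**5. Spillover.** If only 19A differs (GMC 1 against 2, SD 1.0), another serotype with true PD4 ratio 1.00 reads 1.03 to 1.06 at cross-correlation 0.15 to 0.35.

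**The case against.** The strongest case against is size and convention. The worst PD4 ratio bias above is 0.63 SE, which leaves nominal 95% interval coverage near 90%; at 0.42 SE it is about 93%. The example interval, 0.36 to 0.84, still covers 0.50 and excludes 1. For the pre-dose 4 rate at ρ = 0.7, the shift from −21.4 to −15.7 is 5.7 points against a sampling SE of about 8.8. GMC 1 against 2 for 19A is a chosen unfavourable case. Section 8.5.1 already makes a missed dose 4 a protocol violation, so the per-protocol set openly describes completers. Section 8.3 plans no hypothesis tests. Planned PD3 rates, reverse cumulative curves and discontinuation reasons will make exits visible. Section 8.0 allows a supplemental SAP before unblinding.

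Most of this stands and keeps the point minor. It does not remove it. Knowing that infants left does not show what their leaving did to the later estimates, and in an estimation study the population behind each estimate matters. No supplemental analysis is described for these endpoints.

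A reader might also infer more than the documents support:

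- That the primary comparison or the interims are compromised. The rule acts after the PD3 sample, and the interim immunogenicity endpoints for infants in Table 6 are all PD3.
- That the rule favours V114. Nothing gives PD3 19A by arm; the pull is generally toward no difference, whichever arm is weaker.
- That equal PD3 distributions alone protect the ratio. Equal PD3-to-later relationships are needed too.
- That counting exits as non-responders brackets the true difference. It did for GMC 1 against 2 with equal waning, but with equal PD3 (GMC 2, SD 1.0, ρ = 0.5) and 3-fold against 2-fold waning the truth is −11.3, complete-case −11.0 and non-responder −10.6.

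**Conclusion.** The concern holds as a minor point about the secondary pre-dose 4 and PD4 results, chiefly for 19A. The mechanism follows directly from Sections 5.6 and 5.8 and Table 4. Its size cannot be settled from the documents, which give no 19A GMC, SD, exit rate, waning or correlation. Over the plan's general SD and GMC range with assumed correlations of 0.3 to 0.7, it runs from negligible (GMC 3, SD 0.8) to modest (a true PD4 ratio of 0.50 read as 0.53 to 0.60 for GMC 1 against 2, SD 1.0 to 1.4). The reference value is what the arms would have shown had exited infants stayed unrescued and received dose 4. The rescue rule itself is a welfare provision and is not in question.

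**What to change.** Keep the rescue rule and the planned per-protocol analysis. Label its pre-dose 4 and PD4 tables as describing infants who did not meet the rescue criterion, and show rescue exits by arm and trigger beside them.

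In Section 8.6.1 add a supportive longitudinal model of log IgG at PD3, pre-dose 4 and PD4 using all infants with a PD3 result, for 19A first. For other serotypes also include PD3 19A. State that the result extrapolates below the cut and that performance was checked only for 19A.

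That check covered PD4 under the 19A trigger with a common slope: 4,000 simulated trials, 45 per arm, GMC 1 against 2. At SD 1.0 and ρ 0.3/0.5/0.7, complete-case gave 0.528/0.546/0.568 and the model 0.501/0.500/0.500, with the SE of the log ratio rising from 0.219/0.210/0.208 to 0.224/0.216/0.218. At SD 1.4, ρ 0.7, it was 0.599 against 0.499, SE 0.293 to 0.311. If the slope below the cut were really zero or double (ρ 0.7), the model would still give about 0.50 against a truth of 0.52 or 0.48 (SD 1.0), or 0.54 or 0.46 (SD 1.4).

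Optionally, add a pre-dose 4 response-rate table that counts an exited infant as a non-responder for each serotype below 0.35 at PD3. State a rule for exited infants at or above 0.35 on that serotype (for example, left missing). Present it as a sensitivity analysis, not as a bound on the between-arm difference.

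The cost is several extra model fits across serotypes, estimates that depend on the model, and an SE about 2 to 6% larger. Visits, blood draws and rescue doses do not change.
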